Full Title:	Phase II randomized trial of PD-1/PDL-1 axis blockade versus PD-1/PDL-1 axis blockade plus radiotherapy in metastatic genitourinary (renal/urothelial) malignancies
Short Title:	Immunotherapy Plus Radiotherapy in Genitourinary Malignancies
Clinical Phase:	Phase II
Principal Investigator:	[name], M.D. .
Sample Size:	N = 112
Accrual Ceiling:	129
Study Population:	Eligible patients have metastatic renal cell carcinoma/urothelial carcinoma with at least 2 measurable sites of disease.
Accrual Period:	We expect to accrue up to 112 patients over three years and at an accrual rate of approximately 40 patients per year.
Study Design:	Eligible patients have metastatic renal cell carcinoma/urothelial carcinoma with at least 2 measurable sites of disease. All eligible patients will be randomly assigned to immunotherapy (Nivolumab/Atezolizumab/Pembrolizumab) versus immunotherapy (Nivolumab/Atezolizumab/ Pembrolizumab) plus radiotherapy, 10 Gy x3 (conformally or by IMRT/IGRT to maximally spare normal tissue), to one of their measurable lesions. For patients assigned to the immunotherapy plus radiotherapy arm, immunotherapy treatment starts with the first radiotherapy fraction. Nivolumab will be given every 2 weeks for patients with metastatic renal cell cancer and Atezolizumab (flat dose 1200mg) or Pembrolizumab (flat dose 200mg) will be given every 3 weeks for patients with metastatic urothelial cancer. Patients will be re-imaged at 9 week (year 1) or 12 week (years 2-3) intervals and evaluated for response (defined as an objective response of measurable metastatic sites outside the radiation field). This response will be evaluated with CT scans in non-irradiated measurable metastatic sites per RECIST version 1.1. Patients will continue to receive their respective immunotherapies for up to three years or until disease progression or until a dose limiting toxicity is reached.

Study Duration: *Participants will have approximately up to 25-35/yr visits and a follow-up for up to 3 years.*

**Study Agent/
Intervention:**

Patients with metastatic renal cell carcinoma will receive Nivolumab intravenously at a flat dose of 240mg every two weeks. Infusions will be given over 60 minutes (not bolus or IV push). Patients will continue to receive infusions every two weeks for up to three years or until disease progression or until a dose limiting toxicity is reached.

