15.0 Study Procedures and Observations - Nivolumab Alone and Nivolumab plus Radiation

Procedure	Screening Visit (- 28 days)	Day 1 ^h	Day 3 ^h	Day 5 ^h	Day 15 ^h	Day 29 ^h	Day 43 ^h	Day 57 ^h	Day 63 (+/-7 days)	F/UQ 9wks (±7days) for first year ^k	Follow up Q12 weeks (±7days) after 1 st year ^k years 2 and 3
Informed Consent	X										
Inclusion/Exclusion Criteria	X										
Medical History	X										
Pregnancy Test	X	X ^a				X ^a	X ^a	X ^a	X ^a		
Physical Examination Complete	X										
Physical Examination Limited		X				X	X	X	X	X	X
Vital Signs	X	X				X	X	X	X	X	X
Adverse Events Assessment	X	X				X	X	X	X	X	X
Serum Chemistry ^b	X	X				X	X	X	X	X	X
Hematology ^b	X	X				X	X	X	X	X	X
Urinalysis	X	X				X	X	X		X	X
CT (Chest, Abdomen, Pelvis) ⁱ	X								X	X ^d	Q 12 W
MRI Brain ⁱ	X										
Nivolumab infusion^j - ARM A		X			X	X	X	X			
Radiation Therapy^e - ARM B		X	X	X							
Endocrine Panels ^c	X				X	X	X	X			
Genomic Bloods/T-cell collection		X ^f				X ^f		X ^f			
Tumor biopsies	X ^g								X ^g		

a. Before each infusion.

b. SOC labs (COMP, CBC w/diff).

c. TSH, T3, T4

d. Scans day 63 ± 7.

e. Radiation is given to one, randomly selected lesion 30 Gy in 3 fractions of 10 Gy each (ARM B only)

f. to be collected PRIOR to infusion on days 1, 29 and 57.

g. Optional biopsy done at Day 63 (±7 days).

h. infusions will have a ± 3 day window.

i. prior scans will be valid until the screening period of 28 days

j. infusions will be ±24hrs from Day 1 of radiation. k. Patients will come off-study if they have disease progression. Patients will be followed for 30 days from the day they come off-study.

1.12 16.0 Study Procedures and Observations - Atezolizumab Alone and Atezolizumab plus Radiation

Procedure	Screening Visit (- 28 days)	Day 1 ^h	Day 3 ^h	Day 5 ^h	Day 22 ^h	Day 43 ^h	Day 64 ^h	Day 63 (+/-7days)	F/UQ 9wks (±7days) for first year ^k	Follow up Q12 weeks (±7days) after 1 st year ^k , years 2 and 3
Informed Consent	X									
Inclusion/Exclusion Criteria	X									
Medical History	X									
Pregnancy Test	X	X ^a			X ^a	X ^a	X ^a	X ^a		
Physical Examination Complete	X									
Physical Examination Limited		X			X	X	X	X	X	X
Vital Signs	X	X			X	X	X	X	X	X
Adverse Events Assessment	X	X			X	X	X	X	X	X
Serum Chemistry ^b	X	X			X	X	X	X	X	X
Hematology ^b	X	X			X	X	X	X	X	X
Urinalysis	X	X			X	X			X	X
CT imaging (Chest, Abdomen, Pelvis)	X							X	X ^d	Q 12 W
MRI Brain	X									
Atezolizumab/Pembrolizumab infusionⁱ - ARM A		X			X	X	X			

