17.3.2 Safety Assessments

All patients who receive at least one dose of Immunotherapy will be considered evaluable for safety parameters. Additionally, any occurrence of a SAE from time of consent up to and including follow-up visits will be reported. Refer to safety reporting section 6.2

Safety will be evaluated for all treated patients using the NCI CTCAE version 4.03 (<http://ctep.cancer.gov>). Safety assessments will be based on medical review of AE reports and the results of vital sign measurements, physical examinations and clinical laboratory tests.

1.12.1.1 17.4 Criteria for Evaluation

1.12.1.1.1 17.4.1 Safety Evaluation

This protocol will be monitored by the WCM Data Safety Monitoring Committee which oversees the safety of all WCM investigator initiated clinical trials. The trial will be monitored for all adverse events, laboratory abnormalities, and serious adverse events at least once every 12 months. In addition, serious adverse events are monitored for all studies on a monthly basis.

1.12.1.1.2 17.4.2 Efficacy Evaluation

For the purposes of this study, patients should be re-evaluated for response every 9 weeks, in year 1, every 12 weeks in years 2 and 3. Confirmatory scans may also be obtained 4 weeks following initial documentation of objective response or progressive disease.

Response and progression will be evaluated in this study using the international criteria proposed by the Response Evaluation Criteria in Solid Tumors (RECIST) guideline (version 1.1). Patients will be followed for scans every 9 weeks for the first year or until disease progression and every 12 weeks after the first year or until disease progression.

Measurable and non-measurable lesions:

- Measurable disease: Measurable lesions are defined as those that can be accurately measured in at least one dimension (longest diameter to be recorded) as ≥ 20 mm (≥ 2 cm) by chest x-ray or as ≥ 10 mm (≥ 1 cm) with CT scan, MRI, or calipers by clinical exam. All tumor measurements must be recorded in millimeters (or decimal fractions of centimeters).
- Malignant lymph nodes: pathologically enlarged and measurable lymph node must be ≥ 15 mm (≥ 1.5 cm) in short axis when assessed by CT scan (CT scan slice thickness recommended to be no greater than 5 mm [0.5 cm]). At baseline and in follow-up, only the short axis will be measured and followed.

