- AEs should be followed to resolution or stabilization, and reported as SAEs if they become serious. This also applies to subjects experiencing AEs that cause interruption or discontinuation of immunotherapy, or those experiencing AEs that are present at the end of their participation in the study; such subjects should receive post-treatment follow-up as appropriate.
- All SAEs must be collected which occur within 30 days of discontinuation of dosing or completion of the patient's participation in the study if the last scheduled visit occurs at a later time. In addition, the Investigator should notify WCM of any SAE that may occur after this time period which they believe to be certainly, probably, or possibly related to immunotherapy.

1.16.1.8 21.8 Pregnancy

Sexually active women of childbearing potential must use an effective method of birth control during the course of the study, in a manner such that risk of failure is minimized.

Before enrolling women of childbearing potential (WOCBP) in this clinical trial, Investigators must review the guideline about study participation for WOCBP which can be found in the GCP Manual for Investigators. The topics include the following:

- General Information
- Informed Consent Form
- Pregnancy Prevention Information Sheet
- Drug Interactions with Hormonal Contraceptives
- Contraceptives in Current Use
- Guidelines for the Follow-up of a Reported Pregnancy

Prior to study enrollment, WOCBP must be advised of the importance of avoiding pregnancy during trial participation and the potential risk factors for an unintentional pregnancy. The subject must sign an informed consent form documenting this discussion.

All WOCBP MUST have a **negative** pregnancy test within 72 hours **prior** to receiving immunotherapy. The minimum sensitivity of the pregnancy test must be 25 IU/L or equivalent units of HCG. If the pregnancy test is positive, the subject must not receive nivolumab or atezolizumab and must not be enrolled in the study.

In addition, all WOCBP should be instructed to contact the Investigator immediately if they suspect they might be pregnant (e.g., missed or late menstrual period) at any time during study participation.

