Forty patients per year will be randomized to the trial over ~ 3 years of accrual, assuming an accrual rate of approximately 20 patients per year for each cohort (see study calendar).

1.24.1.1 29.1 Statistical analysis

Both arms will run in parallel but will be analyzed separately. When the target accrual is met for a cohort, it will be closed to accrual even though other cohorts may still be accruing. Analyses will be done separately for each arm. Analyses will be similar for the two arms.

The primary objective of this study is the comparison of best overall response rates between each arm after start of treatment. Fisher's Exact test will be used to estimate 95% confidence intervals for the difference and to perform a one-sided test with an alpha level of 20%. Response rates for each arm will also be estimated at this level. With 56 patients treated under each modality, if the true responses are 20% and 40% in the immunotherapy alone and immunotherapy and radiation arms, respectively, we have a 90% probability of detecting a difference between modalities. Secondary objectives include time to disease progression and mortality. Median times for these events will be estimated with 95% confidence intervals. Graphical summaries will include Kaplan-Meier curves and log-rank tests which will be used to detect differences between treatments. Median survival and progression times will be estimated if sufficient events are observed. Cox proportional hazards regression will be used to account for baseline characteristics. Stratified exploratory analyses by type of cancer (renal cancer cell carcinoma or urothelial carcinoma) will also be performed.

Toxicities will be summarized per arm and prepared using Chi-square or Fisher's Exact tests, where appropriate.

Patient and disease characteristics will be summarized and compared at randomization between the two treatment arms using descriptive statistics and graphical displays. Although randomization will remove systematic biases we will test for differences in arms using Chi-square or Fisher's exact methods for categorical variables and t-tests or Kruskal-Wallis tests (with appropriate transformations of data if necessary for continuous variables). Differences in RECIST outcomes within each patient comparing non-irradiated and irradiated lesions will be summarized. Similar techniques will be used for exploratory analyses of the following:

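### Toxicity is compared only as crude proportions, although time at risk depends on progression; add exposure by arm and cumulative incidence at common times

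*Combined protocol and SAP*

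**What the plan says.** Section 1.2 makes the toxicity of the two treatment groups a secondary objective. Section 29.1 gives its analysis in one sentence: "Toxicities will be summarized per arm and prepared using Chi-square" or Fisher tests. The plan names no time window, person-time, time-to-first-event method, or summary of doses or time on drug. Kaplan-Meier curves, log-rank tests and Cox models are planned only for progression and survival; mixed models and GEE only for immune measures.

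The Protocol Summary (Study Design) continues immunotherapy "for up to three years or until disease progression or until a dose limiting toxicity is reached". The footnotes to the procedure tables (sections 15.0 and 16.0) state "Patients will come off-study if they have disease progression" and "Patients will be followed for 30 days from the day they come off-study". Section 21.7 adds "All SAEs must be collected which occur within 30 days of discontinuation of dosing", or up to the end of participation if that is later; after that, only events judged related are to be notified.

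**The concern.** Both exposure to drug and the period in which events are recorded end soon after progression, which is itself an efficacy outcome. The trial is designed around a doubling of response. If that happens, Arm B patients stay on immunotherapy and under observation longer, and the proportion with any event can rise even if radiotherapy adds no toxicity. If Arm B instead progresses sooner, its shorter observation can mask added harm. In either case a chi-square or Fisher test on crude proportions cannot separate the toxicity of radiotherapy from a difference in time at risk.

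**Working it through.** **The plan's own figure.** The plan states no figure for toxicity. Its response assumptions are consistent: a one-sided Fisher exact test with 56 per arm, 20% against 40% and alpha 0.20 has exact power 0.902, against the stated 90%. Those response rates are used below.

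**Inputs from the documents.** Responders 20% (Arm A) and 40% (Arm B); 56 per arm; treatment cap 36 months.

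**Assumed, because the documents do not give them.** Exponential time on drug with mean 4-6 months for non-responders and 15-20 months for responders; hazard h of a first event 3-5% per month while on drug, the same in both arms. The 30-day tail is left out.

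**Formula.** For mean time on drug m, the chance of an event on drug by month c is

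F(m, c) = [h / (h + 1/m)] × [1 − exp(−(h + 1/m) c)].

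Arm A is 0.8 F_N + 0.2 F_R and Arm B is 0.6 F_N + 0.4 F_R (N non-responders, R responders), so B − A = 0.2 (F_R − F_N). Radiotherapy has no effect on toxicity in this model.

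**Example, h = 0.04, means 4 and 20 months, c = 36.**
- F_N = 0.04/0.29 × 1.000 = 0.138
- F_R = 0.04/0.09 × 0.961 = 0.427
- Arm A 19.6%, Arm B 25.4%; difference 0.2 × 0.289 = 5.8 points.
- Mean time on drug is m[1 − exp(−36/m)], about 4.0 and 16.7 months, giving 6.5 months in Arm A and 9.1 in Arm B.

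This pair of means gives the largest gap at that hazard. If risk stops at month 6 or 3, set c to 6 or 3:

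| Risk lasts | Smallest (means 6 and 15, h = 0.03) | Largest (means 4 and 20, h = 0.05) |
|---|---|---|
| Whole treatment | 0.2 × (0.301 − 0.152) = 3.0 points | 0.2 × (0.486 − 0.167) = 6.4 points |
| 6 months | 0.6 points | 1.7 points |
| 3 months | 0.2 points | 0.6 points |

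**Significance.** For 19.6% against 25.4% with 56 per arm, the 95% half-width is 1.96 × √(0.196×0.804/56 + 0.254×0.746/56) = 15 points. A two-sided Fisher test at 0.05 (assumed; the plan gives no level for toxicity) rejects in 4-8% of trials under constant hazard, against about 3% when the proportions are equal.

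**Second model.** Here responders' time on drug is taken from the nivolumab figures in section 3.4: 3.0 months to response plus an exponential with median 23.0 months. Non-responder medians of 2, 4 or 6 months and Arm A toxicity of 10%, 20% or 47% are assumed (47% is the serious adverse reaction figure in section 3.6.11), and one month of follow-up is added. With equal toxicity per unit time, Arm B is higher in all 36 scenarios:
- constant hazard: 2.2 to 10.5 points
- declining hazard (Weibull shape 0.5): 1.2 to 6.5
- risk ending at 6 months: 0.5 to 4.5
- risk ending at 3 months: 0.1 to 1.6

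The same Fisher test rejects in 2-14% of trials.

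**Check of remedies.** In the second model, restricting to the first 3 months cuts the spurious difference to 0-1.6 points. An exposure-adjusted rate gives a B/A ratio of 0.99-1.01 under constant hazard but 0.69-0.91 when toxicity is front-loaded, so Arm B would look falsely safer.

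At 12 months the handling of progression matters. In the example above, counting progression as a competing event gives 0.2 × (0.294 − 0.134) = 3.2 points, so part of the exposure effect remains. Censoring at progression gives 1 − exp(−0.04 × 12) = 38% in both arms, provided progression and toxicity are independent.

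**The case against.** Crude proportions are a valid description of the total toxicity burden of each strategy, and that stands: what is missing is a companion analysis.

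The size also depends on when events occur. Section 4.5 gives early atezolizumab onsets: pneumonitis median 2.6 months (latest 4.2), hepatitis median 1.1, colitis or diarrhea median 1.7 (latest 3.1). For such events the artefact is small. Section 20.0 also keeps patients without rapid deterioration on treatment through tumor increases before week 12, which narrows early differences in exposure. Against this, section 3.6 reports nivolumab pneumonitis as late as 22.3 months and rash as late as 25.8, so late events cannot be set aside.

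A reader might infer that Arm B will show more toxicity simply because its patients stay on drug longer. The documents do not support that. It needs risk to persist through treatment and radiotherapy to work, and an Arm B excess could equally be real radiotherapy toxicity.

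A reader might also infer from "All patients who receive at least one dose of Immunotherapy will be considered evaluable for safety parameters" that an irradiated patient who was never infused is lost to the safety analysis. The same section says that safety is evaluated in all treated patients, so this is a rare matter of wording and no part of the point.

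**Conclusion.** The gap is real and cheap to close. Time at risk depends on the efficacy outcome, and nothing in the plan describes or accounts for it. With equal toxicity per unit time and the assumed exposures and hazards, the spurious Arm B excess is about 3 to 6 points under constant hazard, 0.6-1.7 points if risk ends at 6 months and under 1 point if it ends at 3 months. Longer responder exposure or a higher base rate makes it larger, as the second model shows. The direction reverses if Arm B progresses earlier. The artefact would seldom produce a significant test by itself. The consequence is a distorted estimate for a secondary objective; the primary response comparison is untouched.

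**What to change.** In section 29.1:
- Keep the crude table and label it as total burden per strategy.
- Report time on drug and number of doses by arm.
- Compare arms on cumulative incidence of first event (for example grade 3 or higher, and immune-related) at prespecified common times such as 90 days and 12 months.
- State for each analysis whether death and off-study progression are competing or censoring events. The competing-event version describes risk as experienced; the censored version is closer to risk while on drug.
- Give exposure-adjusted rates as support only, with the caveat that they mislead when toxicity is front-loaded.

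The end of the observation window also needs one definition. Progression takes patients off study in the table footnotes but is absent from the lists in sections 12.3 and 17.2; these should be reconciled.

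The cost is a little more analysis work and no new visits. Onset dates must be recorded: section 21.4 describes a patient-specific log without listing its fields. The change should be fixed before toxicity is compared by arm.

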Patients with metastatic urothelial cancer will receive Atezolizumab intravenously at 1200mg every three weeks or Pembrolizumab at a flat dose of 200mg every three weeks (Physician's discretion). Patients will continue to receive infusions every two or three weeks for up to three years or until disease progression or until a dose limiting toxicity is reached.

Patients randomized to the radiotherapy arm will receive radiation every other day. A dose of 10 Gy x3 days will be administered.

Primary Objectives: The primary aim is to estimate the difference in best overall response (BOR; time frame: 96 weeks) rates using RECIST version 1.1, in patients with metastatic renal cell/urothelial carcinoma when treated with immunotherapy alone and immunotherapy plus radiotherapy (to a single metastatic site).

[figure not shown]
Secondary Objectives: The secondary aims are: 1) to estimate the median progression free survival and the median overall survival for patients treated with immunotherapy and immunotherapy plus radiotherapy, and 2) to assess the toxicity (per CTCAE version 4.0) of patients treated with immunotherapy and immunotherapy plus radiotherapy.

**Exploratory
(Correlatives)
Objectives:**

Exploratory analyses will include: 1) examination of an association between clinical responses and anti-tumor immune responses (cellular and humoral responses) and 2) comparison of T cell subsets within tumors and in the peripheral blood at baseline versus at the time of response evaluation.

Endpoints: The primary endpoint will be BOR (time frame: 96 weeks) rates as evaluated using RECIST version 1.1. Other end points include progression free-survival and overall survival.

SCHEMA
Please see study calendar (section 14.0) for additional screening procedures and treatment windows

- *Renal cell cancer patients – Nivolumab (flat dose of 240mg) q2 weeks up to 3 years. Immune labs to be drawn prior to infusion on Days 1, 29 and 57.
- *Urothelial cancer patients – Nivolumab (flat dose of 240mg) q2 weeks up to 3 years or Atezolizumab (1200mg) q3 weeks up to 3 years or Pembrolizumab (flat dose of 200mg) every 3 weeks up to 3 years. Immune labs to be drawn prior to infusion on Days 1, 43 and 64.
- Radiation (10 Gy x3 fractions) will be delivered on days 1, 3 and 5.
- ‡ MRI brain for patients in the RENAL Cancer cohort only.

Table of Contents

DOCUMENT HISTORY : 6

SUMMARY OF CHANGES : AMENDMENT 1 DATED 12.15.2016 6

PROTOCOL SUMMARY 7

SCHEMA..... 9

1.0 Study Objective 13

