The system provides audit trails that track creation and modification of records that include user ID and timestamp. Once entered, the data is subjected to validation procedures that are executed either immediately or upon saving the eCRF page or during the batch validation process. Validation failures that are identified before the page is saved can be corrected immediately. Validation failures during saving of the eCRF page and during batch validation processes will generate a discrepancy. Depending on the database account privileges, the data managers may be able to correct a discrepancy or if not, route it to the project data manager at WCM who can take appropriate action to correct the problem. Data clarification forms can also be printed out when necessary to be sent to the project data manager. Once the discrepancy is closed, by marking “resolved” or “irresolvable”, the data is marked clean and an audit trail is generated by the system.

All key end points will be source verified by a second person and errors will be corrected. Once the data is verified and all discrepancies are closed, the data can be locked/frozen. Locking and freezing can be done at different granular levels and will follow institutional SOPs and any specific requirements for the project.

Security measures that will be taken in order to protect patient data will include firewall technology and database level security which will be achieved by assigning roles and privileges to different levels of users and by requiring that the users authenticate themselves using user ID and password. Additional security for data transfer between remote clients and servers will be achieved by using digital certificates/SSL. All data will be backed-up to tape periodically according to the Institutional SOPs. All data will be stored for at least 5 years following the termination of this study.

1.24 29.0 Statistical Considerations

112 patients will be randomly assigned in a 1:1 ratio to treatment with immunotherapy (Nivolumab or Atezolizumab) or to treatment with immunotherapy (Nivolumab or Atezolizumab) plus radiotherapy in this phase II trial. With 56 patients per group, if the expected response rate (PR or CR) is 20% with immunotherapy alone, we can detect a response rate of 40% for immunotherapy plus radiotherapy with a 1-sided alpha of 20% and a power of 90%.

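### Beyond per-arm summaries, the only planned between-arm toxicity comparison is a test with no stated level and no difference or interval; at 56 per arm a non-significant result says little about added harm

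*Combined protocol and SAP*

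**What the plan says.** The Protocol Summary lists as a secondary aim "to assess the toxicity (per CTCAE version 4.0) of patients treated with immunotherapy and immunotherapy plus radiotherapy", and section 1.2 repeats the aim. The analysis is in section 29.1: "Toxicities will be summarized per arm and prepared using Chi-square or Fisher's Exact tests, where appropriate". The word 'prepared' is presumably a slip for 'compared'. The sentence gives no test level, sidedness, toxicity endpoint, difference estimate or interval.

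The same section treats response differently: "Fisher's Exact test will be used to estimate 95% confidence intervals for the difference". The response test itself is one-sided at 20%. The section also plans 95% intervals for the median times to progression and death.

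The trial is sized on response alone. Section 29.0 states that "112 patients will be randomly assigned in a 1:1 ratio" and sets the design "with a 1-sided alpha of 20% and a power of 90"%.

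Other safety provisions concern conduct. Section 17.3.2 bases safety assessment on medical review of adverse events, examinations and laboratory results. Section 27.0 has the DSMB review cumulative data annually. Section 27.1 has the study team review adverse events monthly, with a copy to the statistician, and sends the DSMB a final report. The stopping rules in section 27.2 are holds for individual patients, with no between-arm threshold.

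**The concern.** The trial adds radiotherapy to an immunotherapy backbone, so its safety question is how much toxicity the addition brings. A significance test answers a different question: whether an excess has been demonstrated. In a trial sized for a 20-point response difference at a lenient one-sided 20% level, many real excesses would give a non-significant toxicity test. Without a difference and its interval, the planned analysis would not show how large an excess is still compatible with the data. Section 29.1 recognises this need for response and for the medians, but not for toxicity.

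**Working it through.** **Inputs from the documents.** 56 per arm, response rates of 20% and 40%, one-sided 20% level, 90% power (sections 29.0 and 29.1). The safety set is everyone with at least one dose of immunotherapy (17.3.2), taken here as about 56 per arm. One background rate is used as an anchor: immune-mediated pneumonitis on nivolumab, 4.4% (18/406, section 3.6.1).

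**Assumptions, because the documents are silent.** Toxicity test level: two-sided 5%, with one-sided 20% as a sensitivity case. Control toxicity rates: 5% to 20%.

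**Step 1: reproduce the plan's own figure.** With z = 0.8416 (one-sided 20%) and 1.2816 (90% power), the uncorrected size is

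n = [0.8416·√(2·0.3·0.7) + 1.2816·√(0.2·0.8 + 0.4·0.6)]² / 0.2² = (0.545 + 0.811)² / 0.04 ≈ 46.

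The continuity correction (n/4)·[1 + √(1 + 4/(n·0.2))]² takes this to 56 per arm, as stated. Exact enumeration of the one-sided 20% Fisher test at 56 per arm gives power 0.902, so a true 20% versus 40% is missed 10% of the time.

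**Step 2: miss rates for toxicity.** For true rates pA and pB, with b the binomial probability:

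miss = 1 − Σ b(xA; 56, pA)·b(xB; 56, pB), summed over all tables with xB > xA and p-value at or below the level.

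| True rates, A vs B | Chi-square, two-sided 5% | Fisher, two-sided 5% | Fisher, one-sided 20% |
|---|---|---|---|
| Doubling: 5% vs 10% | 84% | 92% | 58% |
| Doubling: 10% vs 20% | 68% | 78% | 35% |
| Doubling: 15% vs 30% | 51% | 61% | 19% |
| Doubling: 20% vs 40% | 35% | 43% | 10% |
| Tripling: 5% vs 15% | 57% | 71% | 25% |
| Tripling: 10% vs 30% | 22% | 31% | 5% |
| Tripling: 15% vs 45% | 5% | 8% | under 1% |

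Chi-square is uncorrected. At the protocol's pneumonitis rate, a doubling (4.4% to 8.8%) is missed 86% of the time by chi-square and 94% by Fisher, both two-sided 5%. A tripling (4.4% to 13.2%) is missed 62% and 76% of the time.

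**Step 3: what a non-significant result leaves open.** The Newcombe upper limit is d + √[(uB − pB)² + (pA − lA)²], where d = pB − pA, uB is the Wilson 95% upper limit for Arm B and lA is the Wilson 95% lower limit for Arm A.

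- 3/56 vs 9/56: d = 0.107, pB = 0.161, uB = 0.278, pA = 0.054, lA = 0.018. Upper limit = 0.107 + √(0.117² + 0.035²) = 0.107 + 0.122, or 0.230 before rounding the parts. Fisher p = 0.12.
- 11/56 vs 18/56: d = 0.125, pB = 0.321, uB = 0.452, pA = 0.196, lA = 0.113. Upper limit = 0.125 + √(0.130² + 0.083²) = 0.125 + 0.155 = 0.280. Fisher p = 0.20.

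Even with identical counts in the two arms, the 95% upper limit on the excess is 9.9 points (3 each), 12.2 points (6 each) or 14.8 points (11 each).

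**The case against.** Four points can fairly be made for the plan.

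- **The miss rates depend on inputs the plan does not give.** This stands. The only test level in section 29.1 is one-sided 20%; if it also applied to toxicity, the doublings would be missed 10% to 58% of the time, and 20% versus 40% would be missed as often for harm as for benefit. A reader might infer that the trial is deliberately easier to pass on benefit than to fail on harm. The documents do not support that, because they state no level for toxicity.
- **The plan never says that non-significance means safety.** This also stands. The objective is to assess toxicity; there is no hypothesis of no excess and no decision rule. That a non-significant test would be accepted as proof of safety is something a reader might infer, not something written.
- **The tests are not the whole safety assessment.** Correct. Per-arm summaries are planned, from which a reader could work out a difference and an interval, and there is continuing medical, study-team and DSMB review. But these provisions do not commit the final analysis to stating the difference or its precision.
- **Low power for adverse events is normal in a phase II trial sized for response.** True, and no larger trial is asked for. Low power is the reason to report an interval rather than rely on a test.

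**Conclusion.** The point holds as a gap in the planned analysis of a secondary objective. Between-arm inference on toxicity is limited to a test without a stated level, with no difference estimate or interval, in a section that plans intervals for the response difference and the medians.

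Its size is conditional. With a two-sided 5% level and control rates of 5% to 20%, both assumed, 56 per arm misses a doubling 35% of the time (20% vs 40%, chi-square) to 92% (5% vs 10%, Fisher). A tripling from 5% is missed 57% to 71% of the time. It would be wrong to extend the 35% to 92% range to triplings in general: 10% versus 30% is missed only 22% to 31% of the time, and 15% versus 45% only 5% to 8%.

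The two worked examples need no assumed control rate: at p = 0.12 and p = 0.20, excesses of 23 and 28 points remain inside the 95% interval. The primary response analysis is unaffected. If toxicity were tested within each tumour cohort, which section 29.1 leaves unclear, numbers per arm would be smaller and power lower; this was not calculated.

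**What to change.** Replace the toxicity sentence in section 29.1 with:

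> For any grade 3 or higher toxicity, and for each toxicity category reported, per-arm proportions and the difference (Arm B minus Arm A) will be given with a two-sided 95% Newcombe interval. The toxicity conclusion will state the upper limit as the largest excess not excluded. Chi-square and Fisher p-values are descriptive, and a non-significant result will not be taken as evidence of no added toxicity.

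The 95% level matches the intervals already planned in that section. No margin is proposed: the documents give none, and an acceptable excess is a clinical judgement. The upper limit is therefore reported, not tested against a threshold.

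The cost is wording and slightly more analysis work, with no new data or patients. The downside for the sponsor is a less favourable safety statement, because the report must name the excess it could not rule out.
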